4.0 PACHYMETRY AND KERATOMETRY

Pachymetry and keratometry of each eye of a subject will be measured at the pre-operative Visit 1 (Screening) and not at any additional study visits unless indicated to assess anomalous results in the post-operative period. The same pachymeter and keratometer should be used for all pachymetry and keratometry measurements, respectively, on each individual eye at a clinical site.

Investigators or designated clinical staff will measure corneal thickness in both eyes of a subject using the topographer / ultrasonic device of their choice. This pachymetry measurement should be done in perpendicular alignment with the central cornea. Each eye corneal thickness will be recorded in the subject source documents and eCRFs, and the TENEO 317 excimer laser default K value of 43.3 D will be used for all eyes during LASIK surgery.

Anterior corneal curvature will be measured for each eye of a subject by keratometry. The axis and degree (in diopters) of the steep and flat axis of the cornea will be recorded.

5.0 CORNEAL TOPOGRAPHY

Corneal topography of subject eyes will be measured at Visit 1 (Screening) and at Visit 5 (Month 1) through Visit 8 (Month 9), or through the last study visit (whichever comes first). Corneal topography is to be measured prior to any study procedures requiring dilation of the eye or any procedure that requires touching the surface of the eye. The same topographer should be used for all measurements on each individual eye at a clinical site. Investigators may use any commercially available corneal topographer to obtain corneal curvature, asphericity, and pachymetry measurements of subject eyes. The make and model of the system used will be recorded in the CRFs. Each subject eye asphericity Q value provided by the topographer instrument will be recorded in the subject source documents and the eCRFs, and the TENEO 317 excimer laser default Q value of -0.20 will be used for all eyes during LASIK surgery.

6.0 PUPIL SIZE

Pupil diameter will be measured at the corneal plane to the nearest \pm 0.1 mm. Pupil size will be measured under photopic conditions or in a darkened room using a handheld infrared pupillometer (preferably a Colvard pupillometer, Oasis Medical, Glendora, CA or VIP-300 pupillometer, Neuroptics, Laguna Hills, CA). If the Neuroptics VIP-300 pupillometer is used, the settings for measurement should be with the Variable Mode *On*, not *Light Off*, and data collected and entered in the EDC system using the Low Mesopic instrument reading.

Pupil measurement will be initiated only after the eye has had time to fully adapt to the testing conditions (approximately 10 minutes). The Teneo 317 Model 2 (ver. 1.28 US SW) excimer laser limits the mesopic pupil sizes that may be treated from a minimum of 4.5 mm to a maximum of 7.0 mm. Operator attempts to enter an OZ outside this range will result in a pop-up message, "out-of-range."

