11.	Use chronic medications by any administration route that may increase risk to the subject or may confound the outcome of the study, including those known to affect wound healing (e.g., corticosteroids, antimetabolites, etc.).	
12.	Are known to have acute or chronic disease or illness (e.g., dry eye, cataract, glaucoma, immuno-compromised, rheumatoid arthritis, clinically significant atopic disease, acne rosacea, etc.) that would increase operative risk or confound the results of the study.	
13.	Are taking medications contraindicated with LASIK such as isotretinoin (Accutane) or amiodarone hydrochloride (Cordarone).	
14.	Are known to be pregnant, lactating, or who plan to become pregnant during the course of the study.	

Bausch + Lomb Study #884	
	15. Have known sensitivity to medications used for standard LASIK.
	16. Have the presence of systemic disease likely to affect wound healing, e.g., autoimmune disease, systemic connective tissue disease, diabetes, or severe atopic disease.
	17. Are participating in any other ophthalmic clinical trial within30 days of screening or during this clinical trial.
	 Have an ocular muscle disorder including a strabismus or nystagmus, or other disorder affecting fixation.
	19. Have a history of or evidence of glaucoma or are a glaucoma suspect.
	20. Eyes with mesopic pupil size > 7.0 mm.
	21. Have a Schirmer's pre-operative test without anesthesia < 4 mm/5 minutes
Planned Study Period and Duration of Treatment	Enrolled subject eyes will undergo LASIK surgery and will be followed for approximately nine months after surgery.
Test Medical Device	Technolas TENEO 317 Model 2 excimer laser is a scanning excimer laser that operates at 193 nm ultraviolet wavelength to photoablate corneal tissue in order to achieve a refractive change.
Study Effectiveness Endpoints	 The percentage of eyes that achieve predictability (attempted versus achieved) of MRSE within ± 0.50 D The percentage of eyes that achieve predictability (attempted versus achieved) of MRSE within ± 1.00 D The percentage of eyes targeted for emmetropia that achieve a UDVA of 20/40 or better
Statistical Methods	Continuous measures will be summarized by the mean, standard deviation, median, minimum, and maximum. Categorical and incidence measures will be summarized by both count and percentage.
	Following multiple imputations of missing data, each primary endpoint will be compared to a corresponding null proportion using a binomial test.

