- 3. Subjects for whom the pre-operative assessment of the cornea indicates that one or both eyes are not suitable candidates for treatment based upon the Investigator's medical judgment.
- 4. Have evidence of retinal vascular disease.
- 5. Have a history of or have active corneal disease or infection (e.g., recurrent corneal erosion syndrome, herpes simplex or herpes zoster keratitis, etc.) in an eye.
- 6. Have a known sensitivity to any study medication.
- 7. Have central corneal scars affecting visual acuity or unstable keratometry with irregular mires in an eye considered for eligibility.
- 8. Have keratoconus, subclinical or forme fruste keratoconus, corneal dystrophy or other corneal irregularity (e.g., irregular astigmatism).
- 9. Have visually significant or progressive cataract in an eye considered for eligibility.
- 10. Had previous intraocular or corneal surgery in an eye considered for eligibility that might confound the outcome of the study or increase the risk to the subject.
- 11. Use chronic medications by any administration route that may increase risk to the subject or may confound the outcome of the study, including those known to affect wound healing (e.g., corticosteroids, antimetabolites, etc.).
- 12. Are known to have acute or chronic disease or illness (e.g., dry eye, cataract, glaucoma, immuno-compromised, rheumatoid arthritis, clinically significant atopic disease, acne rosacea, etc.) that would increase operative risk or may confound the results of the study.
- 13. Are taking medications contraindicated for LASIK such as isotretinoin (Accutane) or amiodarone hydrochloride (Cordarone).
- 14. Are known to be pregnant, lactating, or who plan to become pregnant during the course of the study.
- 15. Have known sensitivity to medications used for standard LASIK.
- 16. Have the presence of systemic disease likely to affect wound healing, e.g., autoimmune disease, systemic connective tissue disease, diabetes, or severe atopic disease.
- 17. Are participating in any other ophthalmic clinical trial within 30 days of screening or during this clinical trial.
- 18. Have an ocular muscle disorder including a strabismus or nystagmus, or other disorder affecting fixation.
- 19. Have a history of or evidence of glaucoma or are a glaucoma suspect.
- 20. Have eyes with mesopic pupil size > 7.0 mm.
- 21. Have a Schirmer's pre-operative test without anesthesia < 4 mm/5 minutes

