6.3 Other Materials

- 6.3.1 Essential Equipment Supplied by the Clinical Site
- 6.3.1.1 Any commercially available femtosecond laser may be used to create corneal flaps prior to performing the LASIK procedure with the TENEO 317 Model 2 (ver. 1.28 US SW) excimer laser. The method of flap production and the make and model of the system used will be recorded in the CRFs.
- 6.3.1.2 Investigators may use any commercially available corneal topographer to obtain corneal curvature, asphericity and pachymetry measurements of subject eyes. The make and model of the system used will be recorded in the CRFs.
- 6.3.2 Materials Provided by the Sponsor
- 6.3.2.1 ETDRS Charts for manifest refraction and visual acuity testing at 40 cm and 4 meters for left and right eyes will be provided by the Sponsor if the Investigator does not have these charts.
- 6.3.2.2 Specular microscopes will be provided by the Sponsor to three or more clinical sites if an Investigator does not have one. The same make and model of specular microscope will be used for an endothelial cell density sub-study at each of the three or more clinical sites.
- 6.3.2.3 A commercially available contrast sensitivity measurement device capable of evaluating binocular mesopic $(3.0 \pm 2.0 \text{ cd/m}^2)$ contrast sensitivity with and without glare at spatial frequencies of 1.5, 3, 6, and 12 cycles per degree (cpd) will be provided by the Sponsor to three or more clinical sites
- 6.3.2.4 Pupillometer capable of measuring photopic and mesopic pupil size by infrared means. A Colvard or Neuroptics infrared pupillometer is preferred

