7.1.1 Pre-operative Visit 1 – Day -60 to -1

Following identification of a potential subject, the Investigator (or designee) will explain the purpose of the study, study procedures, risks/benefits, and study responsibilities to the potential subject. The subject's willingness and ability to meet the follow-up requirements of the study will be determined. Patients that appear to be eligible will be approached for study participation and sign a written Informed Consent Form (ICF) prior to the commencement of study related procedures. The written ICF includes an addendum section that provides subject consent to have photo and video recordings of the eye surgery made. Written informed consent will be obtained prior to the Investigator performing study specific procedures that are NOT part of his/her routine standard of care.

The subject or his/her legal representative and the person obtaining written consent will sign and date the IRB/IEC approved ICF. The original signed document will be retained in the subject records, and a copy will be provided to the subject. Subjects will be given ample time to review the ICF before signing it.

In addition, the applicable privacy regulation requirements must be met (e.g. Health Insurance Portability and Accountability Act [HIPAA] authorization). Research subjects treated at clinical sites located in areas that have additional local requirements will be provided with the required additional local information (e.g. local Bill of Rights).

After providing written informed consent, prospective subjects will be screened to determine whether they meet the entry criteria for the study. Ocular medications used for the study eyes will be documented in the subject source document and the appropriate eCRF, and demographic information will be collected. The pre-operative clinical evaluation will consist of a complete ophthalmic examination conducted at least one but no more than 60 days prior to surgery and will consist of the following:

- Informed Consent Form completion
- Review of inclusion/exclusion criteria

- Pre-operative PROWL questionnaire ³⁴
- Subject demographics
- Subject medical history
- Subject ocular history
- History of contact lens wear
- Pupil size (mesopic)
- Manifest refraction (sphere/cylinder/axis)
- Keratometry
- Specular microscopy (endothelial cell density sub-study)
- Corneal topography
- Uncorrected Near Visual Acuity (UCNVA), photopic conditions

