7.1.2.2 Surgical Technique

Eligible subjects will undergo a LASIK surgical procedure with the TENEO 317 Model 2 (ver. 1.28 US SW) excimer laser device on one or both eyes. In no case should a concurrent bilateral procedure be attempted if there are problems or complications during the surgical procedure for the initial subject eye. The minimum diameter of the optical zone, the degree

of myopia and the magnitude and axis of the astigmatic correction are all determined by the surgeon based on the subjective manifest refraction and mesopic pupil size. The typical optical zones used for TENEO 317 Model 2 (1.28 US) laser treatments of myopia or myopic astigmatism performed outside of the US have been approximately between 6.0 mm and 7.0 mm; however, the 1.28 US software will permit treatments of mesopic pupil sizes within the range of 4.5 mm to 7.0 mm. Operator attempts to enter an OZ size outside this range results in a prompt, "out of range". If the corneal flap created is smaller than the treatment zone size, the procedure will be cancelled. The default treatment parameters (K = 43.3 D, Q = -0.20), not the measured pre-operative keratometry (K) and asphericity (Q) values, will be manually entered into the Teneo 317 Model 2 (ver. 1.28 US SW) excimer laser system. This information is used to develop a laser ablation pattern that removes tissue based on an aspheric algorithm, and additional peripheral tissue removal necessary to achieve the desired post-operative corneal surface asphericity.

Treatment plans for all eyes undergoing LASIK surgery are strongly recommended to be targeted for emmetropia

For expected residual postoperative cylindrical refractive error of ≥ 1.0 D or spherical refractive error of ≥ 2.0 D, the subject should be given the opportunity to experience his/her best spectacle vision with anticipated correction only and be willing to proceed with the surgery.

Details of the surgical technique are described in Appendix C.

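### Protocol Appendix B 6.0 permits a photopic pupil reading, contradicting the mesopic reading that Appendix A, the visit lists, exclusion 20 and the optical-zone rules call for (minor)

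*Protocol*

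**What the plan says.** Appendix B 6.0 of the protocol sets the lighting for pupil measurement: "Pupil size will be measured under photopic conditions or in a darkened room using a handheld infrared pupillometer". It prefers two instruments, the Colvard and the Neuroptics VIP-300. For the VIP-300 only, it fixes the instrument mode and requires "data collected and entered in the EDC system using the Low Mesopic instrument reading". The same section states that the laser "limits the mesopic pupil sizes that may be treated from a minimum of 4.5 mm to a maximum of 7.0 mm".

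The other pupil provisions are these:

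- Exclusion 20 in Protocol 5.3.1.2 reads "Have eyes with mesopic pupil size > 7.0 mm". The Synopsis has it as "Eyes with mesopic pupil size > 7.0 mm", and SAP 6.2.2 repeats it.
- The visit lists in Protocol 7.1.1 (pre-operative) and 7.1.3.4 (Months 3, 6 and 9) name mesopic pupil size.
- Appendix A footnote 7 calls for mesopic conditions at the pre-operative visit, at Months 3, 6 and 9, and at unscheduled visits.
- Protocol 7.1.2.2 says that the minimum optical zone and the intended correction "are all determined by the surgeon based on the subjective manifest refraction and mesopic pupil size".
- Appendix C 4.0 requires the programmed optical zone to be at least as large as the mesopic pupil.
- Protocol 6.3.2.4 specifies the equipment: "Pupillometer capable of measuring photopic and mesopic pupil size by infrared means".
- SAP 6.5.8.11 provides a listing of pupil size and no summary table.

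**The concern.** Appendix B holds the measurement methods, and a footnote to Protocol 7.1.3.4 sends sites to Appendices A and B together for procedural detail. On pupil size the two disagree: A says mesopic, while B offers photopic lighting as one of two options. The protocol states no order of precedence between them.

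The pre-operative reading has two uses. It decides exclusion 20, and it sets the lower bound for the optical zone. By general physiology, which the documents do not discuss, a pupil is usually smaller in bright light than in dim light, so a photopic reading would tend to understate the mesopic size. Two errors could follow:

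- An eye whose mesopic pupil exceeds 7.0 mm, but whose photopic reading does not, would pass exclusion 20.
- An optical zone matched to the photopic reading could be smaller than the mesopic pupil, contrary to Appendix C 4.0.

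The laser's range prompt would not reliably catch either error. It responds to the optical zone entered, not to the lighting under which the pupil was measured, so a value between 4.5 and 7.0 mm is accepted.

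**Working it through.** No arithmetic applies and the plan gives no figure to reproduce. The check sets every pupil-size provision in the protocol side by side.

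| Protocol provision | Role | Lighting named | Limited to one device? |
|---|---|---|---|
| 7.1.1, pre-operative list | what to measure | mesopic | no |
| 7.1.3.4, Months 3, 6, 9 list | what to measure | mesopic | no |
| Appendix A footnote 7 | what to measure, and when | mesopic | no |
| Exclusion 20 (Synopsis, 5.3.1.2) | eligibility limit | mesopic | no |
| 7.1.2.2 | choice of optical zone | mesopic | no |
| Appendix C 4.0 | choice of optical zone | mesopic | no |
| Appendix B 6.0, treatable limits | laser limit | mesopic | no |
| Appendix B 6.0, VIP-300 instruction | method | low mesopic | yes, VIP-300 |
| Appendix B 6.0, general sentence | method | photopic, or a darkened room | no |
| 6.3.2.4 | equipment capability | photopic and mesopic | not a measurement condition |

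1. **Count.** Leaving aside the VIP-300 line, seven provisions rest on mesopic size. Three say what to measure, and four are uses or limits (3 + 4 = 7). One sentence permits a photopic reading. No visit list, schedule entry, eligibility rule or planned analysis calls for one.

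2. **Which half of the sentence conflicts.** A darkened room is compatible with a mesopic reading; photopic lighting is not. The protocol itself treats the terms as different light levels: about 85 cd/m² for photopic acuity testing (Appendix A footnote 8) and about 3.0 ± 2.0 cd/m² for mesopic contrast sensitivity (6.3.2.3 and Appendix B 11.0). Those levels belong to other tests and are cited only to show that the terms are not interchangeable.

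3. **Whether Appendix B corrects itself.** It does for the VIP-300. For the Colvard, or any other handheld infrared device, it has no equivalent instruction. The adaptation period of about 10 minutes in the same section applies to whichever lighting is used, so it does not select one.

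4. **Whether the rest of the protocol corrects it.** Footnote 7 and the two visit lists apply to every device and together cover every scheduled pupil reading. They tell a Colvard user to measure under mesopic conditions. So the plan contradicts itself; it does not leave the lighting open.

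5. **Effect on the analysis.** Pupil size is not an endpoint, does not enter the sample size, and appears in the SAP only as an eligibility criterion and in listings (SAP 6.2.2, 6.5.4.3 and 6.5.8.11).

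**The case against.** The best defence is that the gap is already closed. Footnote 7 is itself a measurement instruction, names no device, and covers the pre-operative visit, Months 3, 6 and 9, and unscheduled visits. The visit lists agree with it. A photopic reading cannot properly satisfy a criterion written for mesopic size, and both optical-zone rules also say mesopic. For harm to occur, a site would have to set all of these aside in favour of half a sentence that also offers a darkened room. The photopic wording may simply carry over from the capability specification in 6.3.2.4. Staff are also trained through a Study Reference Manual (Protocol 5.4), which is not among the documents and may already give the right instruction.

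Most of this stands, and it limits the point. A reader might infer from Appendix B 6.0 that sites without a VIP-300 are free to use photopic readings. The documents do not support that, because the device-neutral mesopic instructions bind those sites too. Nor does the count of seven provisions against one measure risk: repeating the mesopic requirement makes a misreading less likely.

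The defence does not remove the contradiction. Section 6.3.2.4 says what the instrument must be able to do, not how this study measures the pupil. The sentence in Appendix B is a method instruction, in the place where sites are told to look for methods, and one of its two options is wrong for every use the study makes of the reading.

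**Conclusion.** The point holds as a minor internal contradiction. Appendix B 6.0 lists photopic lighting as acceptable where every provision that uses the reading, or says which reading to take, requires mesopic size. The conflict arises for pupillometers other than the VIP-300, and it has an effect only if a site follows Appendix B over Appendix A, the visit lists and the optical-zone rules.

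The risk is small, and the number of eyes affected cannot be estimated: the documents give neither a pupil-size distribution nor a count of sites by pupillometer. The direction of the possible error rests on general physiology. No endpoint, hypothesis test, sample size or planned summary changes. A reader might go further and infer that ineligible eyes were treated or that optical zones were set too small. Nothing in the documents shows that either happened.

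**What to change.** In Appendix B 6.0, delete the photopic alternative so that the sentence requires measurement under mesopic conditions in a darkened room with the handheld infrared pupillometer, whatever the make. Add one sentence saying that this mesopic value is the one used for exclusion 20 and for optical-zone programming. Keep the VIP-300 instruction as it stands. The darkened room should stay, since it is compatible with a mesopic reading.

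The cost is one phrase changed and one sentence added, with nothing to alter in the design, the sample size or the SAP. Protocol 10.7 requires IRB approval before an amendment is implemented, so the change is best carried in the next one. It would govern remaining screenings and remaining Month 3, 6 and 9 readings. How many remain is not stated: enrollment was under way before the March 2020 suspension (Protocol 7.4.1.1), and SAP Section 4 dates protocol Version 8.0 to 19 November 2020.

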7.0 MANIFEST REFRACTION

It is essential that a consistent and standard procedure be used to obtain manifest refraction (MR) measurements. These measurements will be obtained by a qualified ophthalmologist, optometrist, or trained ophthalmic technician only. At no time during the study will auto-refraction be utilized as a final endpoint refraction. Auto-refractor or lensometer readings may only be

utilized to obtain a starting point for the refraction if necessary. The manifest refraction is considered to be the subjectively determined refraction which provides the best corrected visual acuity at a distance of optical infinity.

Each subject must be manually refracted to his/her best correction by an ophthalmologist, optometrist, or a skilled technician using the ETDRS chart at 4 meters with a phoropter or trial frame under photopic lighting conditions. All refractions will be conducted in a manner consistent with the site's standard techniques using 0.25 D steps and utilizing a Jackson cross cylinder method. The resulting manifest refraction obtained using the ETDRS chart at 4 meters is adjusted for optical infinity by subtracting 0.25 D from the sphere value. The 'Chart R' with Sloan letters will be used to obtain the manifest refraction. The manifest refraction which has been adjusted for optical infinity will be documented on the Sponsor-supplied refraction worksheet. The manifest refraction which has been adjusted for optical infinity should be used as the basis for laser refractive treatment.

The resulting manifest refraction will be placed in a trial frame and utilized to obtain BSCVA results. For testing at 4 meters, a +0.25 D must be added to the manifest refraction to correct the testing distance to optical infinity. If for some reason (e.g., dense cataract), MR cannot be obtained, the results should be documented as ND as indicated above and not entered as zeros. In the event of this occurrence, BSCVA will not be tested and the reason for ND will be required in the source document and in the eCRF.

NOTE: Contact lens wearers need to demonstrate a stable refraction (within \pm 0.50 D) in the operable eye(s), as determined by MRSE on two consecutive exam dates. Stability of the refraction is determined under the following conditions:

- Lenses are not worn for at least 2 weeks (rigid or toric contact lenses) or 3 days (soft contact lenses) prior to the first refraction used to establish stability and through the day of surgery;
- The two refractions are performed at least 7 days apart.

Subjects must also be willing to discontinue contact lens wear for the duration of the study.

